- P3. To identify barriers and potential facilitators influencing adherence to oral retinoid therapy PPP measures

8.2 Specific objectives for Healthcare Professionals (HCPs) who prescribe or dispense oral retinoid therapy

The specific objectives for HCPs who prescribe or dispense oral retinoid therapy are the following:

- O1. To describe HCPs' understanding of the oral retinoid therapy PPP measures.
 - To understand the extent to which HCPs are aware of the oral retinoid therapy PPP measures including use of effective contraception and mandated regular interval repeated pregnancy testing, before, during, and after oral retinoid therapy treatment;
 - To describe the content and the format of communication given to WCBP (adult or adolescent) and parents of adolescent WCBP about the oral retinoid therapy PPP measures at the time of prescription, dispensing, and termination (if applicable) of oral retinoid therapy (e.g., educational material given, in which format, reminders given, pregnancy testing communication given, etc);
 - To describe the aspects of the oral retinoid therapy PPP measures that are challenging and not challenging in understanding for HCPs;

- For pharmacists (or any other relevant dispenser of oral retinoid therapy per local practice), to identify what barriers and facilitators in explaining the patient card to WCBPs and ensure its content is well understood;
- To describe the understanding, from the HCPs perspective, of measures to take if a WCBP (adult or adolescent) is planning or becomes pregnant.

O2. To describe the perception of oral retinoid therapy PPP measures by HCPs.

- To describe HCPs' perceptions of the oral retinoid therapy PPP measures, from their perspective and the WCBP's perspectives;
- To describe the HCPs' perceptions of their role in WCBP adhering to PPP measures;
- To explore HCPs' opinions on existing measures to communicate or enhance adherence to current oral retinoid therapy PPP measures;
- To describe HCPs' perceptions of the parents' opinion of the suitability of PPP measures to be applied in adolescent WCBP.

O3. To identify barriers and potential facilitators influencing adherence to oral retinoid therapy PPP measures.

- To describe the extent to which HCPs perceive WCBP (adult or adolescent) adhere to the type and frequency of oral retinoid therapy PPP measures, per oral retinoid therapy type including use of effective contraception and mandated regular interval repeated pregnancy testing;

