- To describe the challenges HCPs perceive in adhering to oral retinoid therapy PPP measures based on WCBP personal and environmental characteristics, organizational characteristics, communications and coordination with other HCPs, and oral retinoid therapy intervention characteristics;
- To describe the transparency HCPs believe adolescent WCBP have with their parents in being sexually active and whether different clinical encounters strategies are implemented to ensure adherence to PPP measures (e.g., individual clinical encounter, etc);
- To understand whether HCPs perceive WCBP (adult or adolescent) may be hesitant to discuss and review some or all aspects of oral retinoid therapy PPP measures with their HCPs;

- To identify the preferred ways for HCPs to communicate information on oral retinoid therapy PPP measures per WCBP type;
 - May include reactions on currently implemented measures in their specific country of residence (e.g., France: use of videos or QR codes)
- To identify currently implemented and potential more effective ways to communicate oral retinoid therapy PPP needs to other HCPs involved in the WCBP's care;
- To identify potential ways to improve the dissemination of PPP information around oral retinoid therapies to WCBP and other HCPs;
- To identify potential ways to improve adherence to PPP measures for oral retinoid therapies in WCBP and HCPs;
- To describe the HCPs experiences of a WCBP becoming pregnant or being pregnant while on oral retinoid therapy, the aspects of the PPP measures that were either not understood or not possible to implement, and potential solutions for prevention in the future.

8.3 Specific objectives for WCBP who recently used or are currently using oral retinoid therapy

The specific objectives for WCBPs who recently used or are currently using oral retinoid therapy are the following:

In WCBP aged 18 to 49 years of age currently or recently using oral retinoid therapy:

O1. To describe the understanding of oral retinoid therapy PPP measures.

- To understand the extent to which WCBP are aware of the oral retinoid therapy PPP measures, including use of effective contraception and mandated regular interval repeated pregnancy testing, (ideally monthly), before, during, and after oral retinoid therapy treatment (including 1 month to 3 years post-treatment when applicable);

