9.1.1 Sample Size and Inclusion/Exclusion Criteria

Qualitative studies do not involve power estimates for sample size, as they rely on establishing saturation to determine when data collection is complete. Saturation in this study will be defined by the achievement of “code saturation” (14). Previous studies involving the assessment of code saturation observed that approximately 9 interviews were sufficient to achieve saturation (14). Sample size recommendations are based on this evidence, while also considering the various subgroups of interest involved in the study and

the anticipated diversity of experiences to be comprehensively captured. Additional information about the adequacy of the sample size and the saturation approach considered for this study is provided in section 1.1.1.1 and further detailed in the Qualitative Analysis Plan, which can be accessed in Annex 4. Qualitative Analysis Plan.

Included oral retinoid therapies in this study are acitretin, isotretinoin and alitretinoin. The target population will include a sample of

- HCPs who prescribe or dispense oral retinoid therapy;
- WCBP who currently or recently used oral retinoid therapy, and;
- Parents of adolescent WCBP who currently or recently used oral retinoid therapy (except alitretinoin).

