9.1.1.1.1 Inclusion Criteria for HCPs Prescribing/Dispensing or Informing on Oral Retinoid Therapy

HCPs will be included in this study if they meet the following criteria:

- Being a licensed medical specialist in one of the study countries who has prescribed oral retinoid therapies to WCBP (e.g., dermatologists, paediatricians, and/or general practitioners) at least once in the last 6 months (n=20 per country);
- Being a registered pharmacist in one of the study countries who dispensed oral retinoid therapy to WCBP at least once in the past 6 months (n=5 to 10 per country);
- Being a registered nurse providing education on PPP measures for oral retinoid therapies to WCBP, if applicable in the target country, at least once in the past 6 months (Poland, Spain, and France only (15); n= up to 5 for France, Poland, and Spain, not applicable for Germany);
- Willing to consent to participate in this study.

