9.2.2.2 Qualitative Data and Analyses

Qualitative data analysis will be done using a qualitative analysis software (e.g., MAXQDA 2022) and will be guided by the PRECEDE-PROCEED implementation science model. This model has two main phases and four internal phases as shown in Table 3. The PRECEDE or evaluative phase, provides a framework for systematically assessing the social, epidemiological, educational ecological, administrative and policy aspects of the topic studied. On the other hand, the PROCEED or intervention phase, used in this study

for describing the barriers and the facilitators for poor adherence to existing PPP measures, recognizes the need to move beyond traditional educational approaches to those that facilitate policy regulation along with improved environmental and organizational resources and services.

Table 3. Eight Phases of the PRECEDE–PROCEED Model

PRECEDE	Predisposing	Phase 1: Social assessment
	Reinforcing	Phase 2: Epidemiological assessment
	Enabling Constructs in Educational Diagnosis	Phase 3: Educational and ecological assessment
	Evaluation	Phase 4: Administrative and policy assessment and intervention alignment
PROCEED	Policy	Phase 5: Implementation
	Regulatory	Phase 6: Process evaluation
	Organizational Constructs in Educational and Environmental Development	Phase 7: Impact evaluation
		Phase 8: Outcome evaluation

The phases of the PRECEDE-PROCEED framework were used to develop moderating guides per respondents that align with the study objective and are included in Annex 8. Semi-structured discussion guides.

The topics discussed align per respondent group, but also to the specific study objectives per respondent shown in sections 8.2 to 8.4 of the current protocol. Grouping of barriers and facilitators across countries and specific oral retinoids in HCPs, WCBP, and parents/caregivers of teenage WCBP will support suggestions for future targeted actions to improve adherence to PPPs.

9.2.2.2.1 Topics to be interviewed with HCPs prescribing or dispensing/educating about PPP to WCBP using oral retinoid therapies

summarises the phases of the moderating guides aligned with the phased of the PRECEDE-PROCEED framework as well as key topics to interview that are related to HCP experiences with oral retinoid therapy PPP measures.

Table 4. Interview topics for HCPs Who Prescribe or Dispense/Educate Oral Retinoid Therapies

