Discussion Guide sections	Phases of the PRECEDE-PROCEED	Specific objectives covered	Specific questions discussed
Participant background	Phase 1: Social assessment	
 • N/A 	
 • Oral retinoid HCP is most familiar with • Number of WCBP using oral retinoids they see in a month
HCP's social assessment of healthcare professionals' knowledge of PPP measures and their relevancy for WCBP	Phase 1: Social assessment	
 • To understand the extent to which HCPs are aware of the oral retinoid therapy PPP measures including use of effective contraception and mandated regular interval repeated pregnancy testing, before, during, and after oral retinoid therapy treatment • To describe the understanding, from the HCPs perspective, of measures to take if a WCBP (adult or adolescent) is planning or becomes pregnant 	
 • Overall level of knowledge and awareness of PPP measures for prescribed/dispensed oral retinoid treatment • Perception of WCBP's health literacy, self-efficacy, and locus of control of health care management influencing PPP adherence for oral retinoids • Overall level of knowledge and awareness of actions to take when WCBP intends to or becomes pregnant while using oral retinoid therapy • Perception of oral retinoid therapy PPP measures (from their perspective, and from the perspectives of WCBP as per their own experiences) • Details on how HCPs assess if WCBP are able to understand the information about PPP measures received and how confident HCPs are about WCBP's ability to understand • Perceived role in adherence of PPP measures
Epidemiological assessment of healthcare professionals' thoughts about factors influencing PPP adherence,	Phase 2: Epidemiological assessment	
 • To describe the aspects of the oral retinoid therapy PPP measures that are challenging and not challenging in understanding for HCPs 	
 • Current adherence to PPP measures when prescribing/dispensing oral retinoid therapy

Template No.: RWI_TP_EPI0016 Revision 1

Reference: RWI_WI_EPI0005

Effective Date: 15Jun2018

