9.4.4.1 Generalizability Limitations Inherent to Qualitative Studies

The recruitment methodologies employed—specifically, direct-to-patient and via HCP referrals—limit participation to individuals who not only have an active email address but are also inclined to express interest through online communication. This subset of the population may not completely embody the diversity and breadth of experiences found in the full spectrum of the targeted population.

Furthermore, this study does not include adolescent WCBP aged 13–17 as participants due to the difficulties associated with obtaining ethical approval for this demographic. Instead, their parents, guardians, or caregivers will be interviewed. While this approach provides valuable insights, it inherently comes with the limitation that these adults may hold different views and perspectives than the adolescents they represent, which could affect the applicability of findings to the actual experiences and needs of the adolescent patients.

Additionally, it is highlighted that acitretin and alitretinoin are not prescribed as commonly as isotretinoin. Yet, it is noted that the former are prescribed more frequently to the older segment of WCBP. As such, to capture a broader range of experiences with these drugs, a specific focus group of older WCBP aged 35 to 49 years has been designated to target the patient population using acitretin and alitretinoin. It is anticipated that this will unveil diverse perceptions of the PPP, although variations are expected among older WCBP with different prescription patterns for acitretin or alitretinoin. These factors must be taken into account when considering the generalizability of the study results across oral retinoids in this study.

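### HCP adherence is to be described per oral retinoid, but nothing in HCP eligibility, strata or stopping secures HCPs with recent acitretin or alitretinoin experience

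*Protocol*

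**What the plan says.** **Objectives.** In Protocol section 8.2, one O3 item asks how far HCPs "perceive WCBP (adult or adolescent) adhere to the type and frequency of oral retinoid therapy PPP measures, per oral retinoid therapy type". Other HCP items concern adolescents and their parents, for example "To describe HCPs' perceptions of the parents' opinion of the suitability of PPP measures to be applied in adolescent WCBP" (O2) and "To describe the transparency HCPs believe adolescent WCBP have with their parents in being sexually active" (O3).

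**Analysis.** Section 9.2.2.2 plans "Grouping of barriers and facilitators across countries and specific oral retinoids in HCPs, WCBP, and parents/caregivers of teenage WCBP" as the basis for suggesting targeted actions.

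**Eligibility.** Section 9.1.1.1.1 admits prescribers of oral retinoids to WCBP ("e.g., dermatologists, paediatricians, and/or general practitioners) at least once in the last 6 months (n=20 per country"). Pharmacists qualify by one dispensing and nurses by one education contact in the same window. No molecule and no patient age group is named, and no specialty has a minimum.

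**Recruitment.** Section 9.1.2.1 monitors HCP recruitment by specialty and country and stops each stratum at its target.

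**Contrast with patients.** Section 9.1.1.2.1 and Table 2 give adult WCBP targets by molecule (60 isotretinoin, 20 alitretinoin, 20 acitretin), plus 10 parents or caregivers of adolescents per country. The interim molecule check in section 9.2.3.2 is defined by the molecules that adult and adolescent WCBP use. It names no HCP group.

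**The concern.** The objective and the planned grouping need HCPs who have recently handled each molecule. The sampling rules do not ask for that. Section 9.4.4.1 states that "acitretin and alitretinoin are not prescribed as commonly as isotretinoin", and the protocol acts on this for patients, with targets and a stepwise boosting plan, but not for HCPs.

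The per-molecule HCP objective could therefore rest on very few informants for acitretin and alitretinoin, or on opinion without recent experience. This matters most for acitretin, because Table 1 gives it post-treatment contraception and testing of 3 years, against 1 month for the other two under the updated measures. HCPs who handle only isotretinoin have no recent experience of that requirement to report.

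The adolescent items share the weakness in a milder form. Section 9.4.4.1 explains that adolescents are not interviewed and that their parents may see things differently. HCPs are the only other source on adolescents, yet none is required to treat any.

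**Working it through.** **Inputs from the protocol**
- HCPs per country: 20 prescribers and 10 dispensers or educators (section 4, Study Size; section 9.1.1.1).
- Countries: four. Alitretinoin is not authorised in Poland (Table 2 note), leaving three for that molecule.
- Benchmark: about 9 interviews for code saturation (section 9.1.1).
- Relative use: acitretin and alitretinoin less common than isotretinoin, with no share stated (section 9.4.4.1).

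**The plan's own figure.** 20 + 10 = 30 HCPs per country, which agrees with the stated 30. Over four countries this is 4 × 30 = 120 HCPs, of whom 4 × 20 = 80 are prescribers. In the three alitretinoin countries it is 3 × 30 = 90 HCPs, of whom 3 × 20 = 60 are prescribers.

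**Which pool applies.** O3 asks per molecule, and section 9.2.2.2 groups by country and by molecule. Neither asks for a result for each molecule within each country. The pools are therefore 80 prescribers for acitretin and 60 for alitretinoin.

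**Assumption.** Let s be the share of eligible prescribers with at least one recent prescription of the molecule to a WCBP. It is shown at 5%, 10% and 20%.

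**Formula.** X ~ Binomial(n, s); expected number = n × s; chance of reaching the benchmark = P(X ≥ 9) = 1 − Σ (k = 0 to 8) C(n, k) s^k (1 − s)^(n − k).

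| s | Alitretinoin, n = 60: expected | P(X ≥ 9) | Acitretin, n = 80: expected | P(X ≥ 9) |
|---|---|---|---|---|
| 5% | 3 | 0.3% | 4 | 2% |
| 10% | 6 | 14% | 8 | 41% |
| 20% | 12 | 87% | 16 | 99% |

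**Complete absence.** At s = 5%, the chance of no experienced prescriber at all is 0.95^60 = 4.6% for alitretinoin and 0.95^80 = 1.7% for acitretin. The likely failure is too few informants, not none.

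**Counting the allied HCPs too.** If pharmacists and nurses had the same share s (a further assumption), P(X ≥ 9) at 5%, 10% and 20% would be 4%, 55% and above 99% for n = 90, and 15%, 86% and above 99% for n = 120. This softens the result at 10% but not at 5%.

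**Adolescent practice.** The documents give no figure on the adult and adolescent split, so no calculation is offered.

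**The case against.** The strongest reply is that s is the share of prescribers with at least one such prescription in 6 months, not the share of prescriptions. A molecule can be uncommon among patients and still familiar to many prescribers. This stands. Shares of 20% or more are possible, and with countries pooled the problem is then largely gone.

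It is also fair that only one of the 18 HCP items in section 8.2 is explicitly per molecule, and that the HCP screener (Annex 6), the HCP discussion guide (Annex 8) and the Qualitative Analysis Plan (Annex 4) are not shown. They may already record molecule, or put the questions molecule by molecule. However, eligibility, strata and stopping are fixed in the protocol text, and there molecule plays no part. Section 9.2.2.1 records specialty, conditions treated and prescribing frequency. These would help to reveal thin coverage at reporting but would not prevent it.

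Three stronger readings are tempting and not supported:
- A reader might infer that the HCP sample will speak almost only about isotretinoin in adults. No age split is given, paediatricians are eligible, and specialty is a monitored stratum.
- A reader might take the Table 4 item "Oral retinoid HCP is most familiar with" as tying the interview to one molecule. It is a background item with no objective attached, and nothing limits the later questions to that molecule.
- A reader might work with the 20 prescribers of one country, where the chance of none at s = 5% is 0.95^20 = 36%. The protocol does not call for results by molecule within country.

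Finally, section 9.1.1 says "Qualitative studies do not involve power estimates for sample size, as they rely on establishing saturation to determine when data collection is complete". That is accepted: the benchmark of 9 is used here only as the protocol's own yardstick. The saturation checks by molecule are defined by patients' use, so they would not flag a shortage among HCPs.

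**Conclusion.** The point holds as a gap between objective and sampling. The protocol asks a per-molecule question of HCPs and plans per-molecule grouping, but nothing visible in it secures HCPs able to answer for acitretin and alitretinoin. It is a risk, not a demonstrated shortfall. On prescribers alone and with countries pooled, the benchmark of about 9 would probably be missed for both molecules at shares up to about 10%, and probably met by 20%. These figures rest on assumed shares, on HCPs being recruited independently of molecule, and on 9 being an adequate yardstick. For adolescents, the missing minimum is a fact of the text, but the documents do not show that a shortfall is likely. This is a cheap improvement worth making before recruitment starts.

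**What to change.** In sections 9.1.1.1.1 and 9.1.2.1, make recent molecule experience and adolescent practice, taken from the HCP screener, monitored recruitment minimums within the unchanged 20 prescribers and 10 allied HCPs per country. Add the screener items if it does not already hold them.

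Set the minimums pooled across countries and tie them to the protocol's own benchmark, with one HCP able to count towards several:
- about 9 HCPs with recent acitretin experience overall;
- about 9 with recent alitretinoin experience across France, Germany and Spain;
- a similar number who treat adolescent WCBP.

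Ask the O3 adherence questions for each molecule the HCP has recently handled. If a minimum is missed, state that HCP conclusions per molecule apply only to the molecules actually covered.

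The cost is at most two screener items and some quota monitoring. No interviews are added, but the last HCP places will fill somewhat more slowly.

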9.1 Study design

This is a non-interventional qualitative cross-sectional study that will be conducted in multiple European countries (i.e., France, Germany, Poland, and Spain). The data will be collected using qualitative interviews.

9.1.1 Sample Size and Inclusion/Exclusion Criteria

Qualitative studies do not involve power estimates for sample size, as they rely on establishing saturation to determine when data collection is complete. Saturation in this study will be defined by the achievement of “code saturation” (14). Previous studies involving the assessment of code saturation observed that approximately 9 interviews were sufficient to achieve saturation (14). Sample size recommendations are based on this evidence, while also considering the various subgroups of interest involved in the study and

the anticipated diversity of experiences to be comprehensively captured. Additional information about the adequacy of the sample size and the saturation approach considered for this study is provided in section 1.1.1.1 and further detailed in the Qualitative Analysis Plan, which can be accessed in Annex 4. Qualitative Analysis Plan.

Included oral retinoid therapies in this study are acitretin, isotretinoin and alitretinoin. The target population will include a sample of

- HCPs who prescribe or dispense oral retinoid therapy;
- WCBP who currently or recently used oral retinoid therapy, and;
- Parents of adolescent WCBP who currently or recently used oral retinoid therapy (except alitretinoin).

9.1.1.1 Inclusion / Exclusion Criteria for HCPs Prescribing/Dispensing Oral Retinoid Therapy

A combination of different HCPs including medical specialists who prescribe oral retinoid therapy (n=20) and allied HCPs who dispense and/or educate WCBP about PPP measures whilst using oral retinoid therapy (n=10) in each of the study countries (France, Germany, Poland, and Spain) will be included if they meet the following inclusion criteria:

